Additionally, statistical modeling will be performed on the secondary endpoint of length of hospital stay, defined as the time from treatment initiation to hospital discharge in hours. Subjects for whom no timepoint could be established (eg, withdrawal of informed consent before reaching the endpoint) will be (right-)censored at the latest timepoint at which it could be established that the endpoint was not reached. The differences in length of hospital stay of active dose regimens versus placebo treatment will be estimated using the accelerated failure time model using appropriate contrasts; as baseline covariates stratification factors, absence/presence of other viral or bacterial infections, and baseline \log_{10} viral load will be added. Treatment effect versus placebo will be reported as acceleration factors including 95% confidence intervals. In case the model assumptions are not adequately met, appropriate sensitivity analyses will be performed as detailed in the SAP. For the secondary endpoint of length of hospital stay, defined as the time from study treatment initiation to readiness for discharge in hours, with readiness for discharge defined by the investigator, an analogous approach will be used. The length of hospital stay from admission to discharge and from admission to readiness for discharge (as defined by the investigator), measured in days, will be analyzed using an analogous approach. Analytical details will be provided in the SAP.

Analysis of the sequencing results of the L-gene or other genes (only if no mutations are seen in the L-gene) will be described in the SAP. Statistical analysis of the viral load, that may be generated with the plaque assay, will be described in the SAP.

Parent/Caregiver-reported Evaluation of Clinical Outcomes

Parent/caregiver-reported eCOA (PRESORS) will be descriptively summarized by treatment group and compared across treatment groups.

Clinician-reported Evaluation of Clinical Outcomes

Clinician-reported eCOA (PRESORS) will be descriptively summarized by treatment group and compared across treatment groups.

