5.3.2. Analysis Methods

Descriptive statistics

The descriptive statistics that will be shown will include the number of subjects, mean, standard deviation, standard error, 95% confidence interval, median, range and interquartile range.

Time-to event variables

All Time-to event variables will be analyzed using Kaplan-Meier estimates analysis, A summary table including number of subjects included in the analysis, number of subjects censored, 25th and 75th percentiles and median time-to event, with 95% confidence intervals based on log-log transformation method, will be presented. The data will be presented graphically using the Kaplan-Meier estimate of the survival function by treatment.

Accelerated failure time (AFT) model

When indicated time-to event variables will be compared between each active treatment group and placebo using an accelerated failure time (AFT) model. The distribution to be used will be determined based on the goodness of fit using Akaike’s information criterion and will be selected from the following parametric families: lognormal, log-logistic, or Weibull. The AFT model will include the fixed, categorical effects for treatment (with placebo as the reference) and stratification factor.

A summary of information from the final AFT model will include parameter estimates and associated standard errors, estimated accelerated failure time ratios versus placebo and associated 95% confidence intervals, and p-values. The survival curves per treatment group of the accelerated failure time model will also be shown.

Logistic regression model

A stratified logistic regression model will be used to analyze the binary outcome, with treatment group and stratification factors as fixed effect, will be used to obtain the odds ratios (95% CI) for each comparison versus placebo.

The odds ratios including 95% confidence interval of active groups versus placebo will be derived from the final model using appropriate contrasts. Exact logistic regression models will be used in case the incidence of the events is low (< 10 events).

Model building procedure

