In the statistical models following predictive covariates and or baseline indicators may be included: baseline \log_{10} viral load, smoking in the environment (yes/no), presence/absence of comorbid diseases, presence/absence of comorbid diseases associated with risk for lower respiratory tract disease, presence/absence of other conditions/therapy of potential interest, days since symptom initiation, RSV subtype, use of corticosteroids, supplemental oxygen at baseline, absence/presence of other viral or bacterial infections and age as continuous variable.

Stepwise forward selection will be used to identify the prognostic factors in combination with backward elimination. A significance value of 0.05 is required for a variable to enter the model and a significance value of 0.10 is required to stay in the model.

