5.3.2.1. RSV RNA \log_{10} viral load qRT-PCR

Log₁₀ Viral Load

Descriptive statistics and mean (SE) graphs will be shown of the \log_{10} viral load actual values and changes from baseline. For exploratory purpose the \log_{10} viral load actual values and changes from baseline will also be shown by sampling method (measured in the mid-turbinate nasal swabs and endotracheal samples from intubated subjects).

Differences on RSV RNA \log_{10} viral load by qRT PCR between treatment groups and by analysis visit will be determined by using appropriate contrasts in the mixed model in which the primary endpoint is modelled. Nominal 95% confidence intervals will be used.

Peak viral load; Rate of decline

The Rate of decline of viral load over the first 24 hours will be analyzed using descriptive statistics including the geometric mean and the coefficient of variation (CV).

The log peak viral load and rate of decline of RSV RNA viral load will be compared for active groups versus placebo groups using a general linear model with treatment and strata included as fixed effects.

Residuals of the final model will be plotted in a normal probability plot.

In case the model does not fit the log peak value data well, the log transformation (ie. the log of log peak viral load) will be considered as dependent variable. The data from the model will be reported as (adjusted) differences in least squares (LS) means (in the case of untransformed data) or (adjusted) geometric mean ratios (in case of log-transformed data) of active dose groups versus placebo, including 95% confidence intervals using appropriate contrasts.

RSV viral load AUC's.

The same model used for the primary analysis will be used to test for a dose response relationship on the viral load AUC until Day 10, until Day 14 and until 1 day after last dose for subjects with treatment extension (if applicable) (respectively $AUC_{1-10Days}$, $AUC_{1-14Days}$ and $AUC_{1-xxDays}$). No corrections for multiplicity will be made, thus the significance level of alpha (α^*) will be kept at 0.05. The differences in these AUCs for active versus placebo will be derived using appropriate contrasts deriving least square mean differences, including the 95% 2 sided confidence intervals.

The sensitivity analysis will be similar as for the primary endpoint, using the calculated viral load AUCs per subject based on the trapezoidal method (AUC_{0-240h} , AUC_{0-336h} and AUC_{0-xxh}) as indicated in section 5.3.1.1.

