5.3.2.3. RSV clinical outcome

Length of hospital stay and time to readiness for discharge.

These time-to event variables will be analyzed as indicated above using Kaplan-Meier analysis, and will also be compared between each active treatment group and placebo using an accelerated failure time (AFT) model. .

Additionally, the time-to event data will be analyzed using the logrank test and Gehan-Wilcoxon method comparing each active treatment to placebo

Duration of intensive care unit (ICU) stay (hours) [Duration]

The duration in the ICU will be analyzed descriptively for all subjects and by subgroup of subjects staying / not staying in the ICU at the time of first dose of study drug.

Requirement for intensive care or supplemental support

The requirement for intensive care unit (ICU) stay, for oxygen supplementation, for noninvasive mechanical ventilation support, for invasive mechanical ventilation support, for supplemental feeding/hydration will be analyzed similarly. These requirement parameters will only be calculated for those subjects that don't require intensive care or supplemental support (depending on the parameter of interest) before first dose of study drug.

The proportion of subjects within the requirement categories (yes and no) will be shown in a frequency tabulation (with corresponding 95% CI) and per treatment group.

In addition, a stratified logistic regression model will be used to analyze the outcome

The analyses of the requirement parameters will answer the question:

Is there a treatment difference in preventing the use of intensive care or supplemental support?

Time to end of intensive care or supplemental support

These time-to event parameters will be analyzed for those subjects that require intensive care or supplemental support (depending on the parameter of interest) before first dose of study drug,

Kaplan-Meier analysis and stratified Gehan test to compare active treatment groups versus placebo will be used.

These time-to event parameters will answer the question:

Is there a treatment difference in the time to no longer requiring intensive care or supplemental support?

While we cannot integrate the results on the requirement for intensive care or supplemental support and the time to end of intensive care or supplemental support they are conceptually linked. We will combine the p-values for both independent tests for the comparison of each active group versus placebo using the method of Liptak^[3].

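### For length of stay and readiness for discharge, the SAP does not fix two covariates that the protocol requires, and its peak and 24-hour decline models omit baseline viral load

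*SAP*

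**What the plan says.** For length of stay from treatment start to discharge, Protocol 11.3 prescribes an AFT model with, "as baseline covariates stratification factors, absence/presence of other viral or bacterial infections, and baseline" log10 viral load. The sentence is a commitment that these will be added, not an option. Readiness for discharge and the two versions counted from admission are to be handled analogously.

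SAP 5.3.2 defines the AFT model once for all endpoints: "The AFT model will include the fixed, categorical effects for treatment (with placebo as the reference) and stratification factor". SAP 5.3.2.3 then says of stay and readiness that they "will also be compared between each active treatment group and placebo using an accelerated failure time (AFT) model", and lists no covariates.

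The other two protocol covariates appear in the SAP 5.3.2 paragraph on model building, which begins "In the statistical models following predictive covariates and or baseline indicators may be included". Baseline log10 viral load and other infections are two of its 11 candidates. They are chosen by a search: "Stepwise forward selection will be used to identify the prognostic factors in combination with backward elimination". The thresholds are p < 0.05 for entry and p < 0.10 for retention.

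For peak viral load and rate of decline, SAP 5.3.2.1 compares active groups with placebo "using a general linear model with treatment and strata included as fixed effects". SAP 5.3.1.1 lets the peak be the baseline record.

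For stay and readiness, SAP 5.3.2.3 adds that "the time-to event data will be analyzed using the logrank test and Gehan-Wilcoxon method comparing each active treatment to placebo". It does not say whether these tests are stratified.

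**The concern.** Length of stay and readiness for discharge are among the more visible clinical outcomes of the trial. For them the two documents give different models, and the SAP version leaves open which covariates the reported acceleration factors will be adjusted for. If that is decided by a significance search, the final model is known only after the outcome data have been used to choose it.

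The peak and decline models raise a matter of precision. The peak is tied to baseline by construction, and decline is a change from baseline. Leaving the baseline value out keeps between-subject variation in the comparison that a variable already measured could remove.

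**Working it through.** **1. The plan's own figure.** The only stated design figure is the power of the primary test: about 97% at 180 subjects and at least 80% at 120. A simulation with the stated assumptions (10,000 runs, 40% early onset, two contrasts, Pocock levels, looks at 90, 120 and 180) gives 96.3% and 85.8%. The figure holds, and this point does not depend on it.

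**2. Fixed model terms side by side.**

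| Analysis | Protocol 11.3 | SAP, fixed terms |
|---|---|---|
| Stay, readiness (AFT) | strata, other infection, baseline viral load | treatment, strata |
| Clinical stability (Cox) | strata, other infection, baseline viral load | the same three |
| Time to undetectable virus (AFT) | strata, baseline viral load; others if significant | treatment, stratum, baseline viral load; others by model building |
| Primary mixed model | includes baseline viral load | includes baseline viral load |
| Trapezoidal AUC (supportive) | not described | treatment, stratum, baseline viral load |
| Peak, rate of decline | no model named | treatment, strata |

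The SAP carries the protocol covariates over for clinical stability and time to undetectable virus, but not for stay and readiness. The protocol allows significance-driven covariates for time to undetectable virus and gives no such permission for stay.

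**3. Two readings of the model-building paragraph.** It speaks of statistical models in general, but the SAP invokes it expressly only for the interval-censored AFT model.
- If it covers stay and readiness, two required covariates become optional.
- If it does not, they are absent.

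Either way the SAP departs from the protocol.

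**4. What selection would do (assumptions; the documents give no covariate effects).** With 11 independent candidates of no prognostic value and entry at 0.05, the chance that at least one enters is 1 − 0.95^11 = 43%.

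A simulation used a log-normal AFT model without censoring, 120 subjects (the expected ITT-i size in SAP 5.1.1), 40 per arm, independent covariates and 1,500 runs per setting. The effect column is the effect of each of the two protocol covariates, in residual SDs.

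| Effect | Baseline viral load kept | Both kept | Some other candidate enters | Type I error, stepwise | Type I error, fixed covariates |
|---|---|---|---|---|---|
| 0 | 6% | 0.1% | 39% | 6.1% | 5.5% |
| 0.15 | 34% | 12% | 37% | 6.1% | 5.1% |
| 0.30 | 87% | 77% | 36% | 5.2% | 4.5% |

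The Monte Carlo standard error of the type I errors is about 0.6 points. At effect 0.30, the SD of the treatment estimate is 0.2406 with strata only and 0.2212 with the protocol covariates fixed, a cut of 1 − 0.2212/0.2406 = 8%. At 0.15 or below there is no clear gain.

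**5. Peak viral load.** Adjusting for a covariate with correlation r to the outcome, given treatment and strata, multiplies the standard error by √(1 − r²).
- r = 0.5: √0.75 = 0.866, a 13% cut.
- r = 0.9: √0.19 = 0.436, a 56% cut.

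**6. Rate of decline.** The same formula, with a correlation between change and baseline of −0.3 to −0.5, gives factors 0.954 to 0.866, a cut of 5% to 13%. Alternatively, assume equal variances at both times and correlation ρ between them. The variance of the change score relative to the adjusted analysis is then 2/(1 + ρ): 1.54, 1.33 and 1.18 at ρ = 0.3, 0.5 and 0.7. The cut in standard error is 1 − √((1 + ρ)/2) = 19%, 13% and 8%.

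**The case against.** Several points on the other side stand.

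- A reader might infer that the SAP discards all the protocol's covariates. It does not: the strata remain fixed, and the other two are named candidates. SAP section 1 also says the SAP is to be read together with the protocol, so the protocol sentence is not expressly revoked. That still leaves two different models for one endpoint.
- A reader might infer that stepwise choice makes the confidence intervals too narrow. The simulation does not show this: 5.2–6.1% against 4.5–5.5% is at most a small inflation. The candidates and thresholds are also stated in advance.
- A reader might infer that the peak comparison mostly reflects chance baseline differences. The documents do not say how often the peak is the baseline record, and randomisation keeps the unadjusted comparison unbiased.
- If the model-building paragraph is general, it may reach peak and decline too; SAP 5.3.2.1 speaks there of a final model and adjusted differences. At r = 0.5 and 120 subjects, baseline would enter with t = 0.5 × √(118/0.75) ≈ 6.3, so almost always. The precision loss for peak would then largely disappear.
- Early virology already has a baseline-adjusted comparison, because the by-visit contrasts come from the primary mixed model. Protocol 11.3 applies the primary method to differences by treatment day and names no model for peak or decline. A conflict with the protocol there is not established.
- A reader might infer that the logrank and Gehan-Wilcoxon tests ignore the strata. The SAP is silent rather than explicit. The tests are additional, and the protocol does not require them.

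**Conclusion.** The point holds in a limited form. For length of stay and readiness for discharge, from treatment start and from admission, the SAP does not fix two of the three covariate sets that the protocol requires. That rests on the text alone and holds under either reading of the model-building paragraph. The main harm is lost pre-specification. The loss of precision there is roughly nil to 8% of the standard error under the assumed effects.

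For peak and decline, omitting baseline leaves avoidable noise: 13% to 56% of the standard error for peak and about 5% to 19% for decline. These figures rest wholly on assumed correlations and shrink if selection would have brought baseline in.

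All of these are secondary analyses. No stated sample size, alpha or power changes. Clinical stability, return to pre-RSV levels and interval-censored time to undetectable virus are not affected. Stratification of the rank tests is a matter of clarity, not an error.

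**What to change.** - In SAP 5.3.2.3, list treatment, stratification factors, other viral or bacterial infection (yes/no) and baseline log10 viral load as fixed terms in the AFT models for stay and readiness, both from treatment start and from admission. Label any stepwise run on these endpoints exploratory.
- In SAP 5.3.2.1, add baseline log10 viral load as a fixed covariate to the peak and rate-of-decline models.
- Optionally, state that the supplementary logrank and Gehan-Wilcoxon tests are stratified by the randomisation strata, as the SAP already does for the Gehan test on intensive care and supplemental support.

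The cost is SAP wording and model statements. The added covariates are already in the SAP's own candidate list, so no new data are needed.

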2.1.2. Endpoints

Primary Endpoint

The primary endpoint is RSV viral load (measured by qRT-PCR in the mid-turbinate nasal swab specimens) AUC from immediately prior to first dose of study drug (baseline) until Day 7.

Secondary Endpoints

The secondary endpoints are:

- Safety/tolerability including AEs, physical examinations, vital signs/peripheral capillary oxygen saturation (SpO₂), ECGs, and clinical laboratory results.
- PK parameters of JNJ-63549109.
- RSV clinical course endpoints:
 - Length of hospital stay from admission to discharge and to readiness for discharge and from study treatment initiation to discharge and to readiness for discharge, with readiness for discharge evaluated by the investigator.
 - Requirement for and duration of intensive care unit (ICU) stay.
 - Requirement for and duration of oxygen supplementation/noninvasive mechanical ventilation support (eg, nasal cannula, face mask, continuous positive airway pressure) and/or invasive mechanical ventilation support (eg, endotracheal-mechanical ventilation or mechanical ventilation via tracheostomy) above pre-RSV infection status.
 - Time to no longer requiring supplemental oxygen above pre-RSV infection status.
 - Time to clinical stability defined as the time from initiation of study treatment until the time at which the following criteria are met: return to pre-RSV infection status (hereafter referred to as “normalization”) of blood oxygen level (ie, without additional requirement of supplemental oxygen compared with pre-RSV infection status), normalization of oral feeding, normalization of respiratory rate, and normalization of heart rate.
 - Time from initiation of study treatment until SpO₂ ≥93% on room air among subjects who were not on supplemental oxygen prior to the onset of respiratory symptoms.
 - Time to respiratory rate, SpO₂, and body temperature return to pre-RSV infection status.
 - Incidence of acute otitis media (defined by the investigator).
- The duration and severity of signs and symptoms of RSV infection as assessed by the PRESORS questionnaire completed by the clinician in the eCOA device.
- RSV viral load as measured by qRT-PCR in the mid-turbinate nasal swab specimens, which will be used to determine the following:
 - RSV viral load over time.

- Peak viral load, time to peak viral load, rate of decline of viral load, and time to RSV RNA being undetectable.
- Proportion of subjects with undetectable RSV viral load at each timepoint.

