1.2.1. Option A

Hospitalized infants and children who are infected with RSV will be randomly assigned to a treatment regimen in this study, with 60 subjects planned per regimen. At least 120 subjects are planned to be enrolled up to a maximum of 180 subjects. An effort will be made to enroll at least 90 subjects aged between 28 days and 24 months and at least 12 subjects aged between 24 and 36 months. The number of subjects with comorbidities will be limited to 20%; additional comorbid subjects aged between 24 and 36 months may be allowed to enroll if the 20% threshold is reached before 12 subjects aged between 24 and 36 months are enrolled into the study.

Subjects will be randomized in a 1:1:1 ratio to Regimen A, B, or C:

- Regimen A (low-dose lumicitabine): a single 40 mg/kg LD (Dose 1) followed by nine 20 mg/kg MDs (Doses 2 to 10) of lumicitabine, administered twice daily.
- Regimen B (high-dose lumicitabine): a single 60 mg/kg LD (Dose 1) followed by nine 40 mg/kg MDs (Doses 2 to 10) of lumicitabine, administered twice daily.
- Regimen C (placebo): those randomized to a placebo regimen are subsequently randomized in a 1:1 ratio (to match volumes) to either:
 - A single 40 mg/kg placebo LD (Dose 1) followed by nine 20 mg/kg MDs (Doses 2 to 10), administered twice daily.
 - A single 60 mg/kg placebo LD (Dose 1) followed by nine 40 mg/kg placebo MDs (Doses 2 to 10), administered twice daily.

An IDMC (refer to Section 3.2, Independent Data Monitoring Committee, for details) will review the safety and PK data once the first 12 subjects and 30 subjects have completed treatment (Day 5/6) to assess if enrollment of additional subjects may safely continue in each arm. After at least 9 subjects have completed treatment with the 60 mg/kg LD/40 mg/kg MD lumicitabine regimen, the IDMC may recommend that sparse PK sampling be used for the other subjects. Subject recruitment and enrollment may continue while the data are being reviewed.

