Viral load status at each time point (categorical)	
Each RSV viral load measurement will be assigned to one of the 3 categories below:
 
 Undetectable (<LOD) Detectable (<LOQ) Quantifiable (\geq LOQ)
Viral load status at each time point (binary)	
Each RSV viral load measurement will be assigned to one of the 2 categories to identify if it is undetectable. Categories will be Yes (1) or No (0).

Time to virus undetectable (hours) [Time-to event]	
The time in hours from initiation of study treatment until the first post baseline time point at which the virus is undetectable in an assessment and after which time no detectable virus assessment follows (= event).
 
For each subject in the ITT-i it will be assumed that the subject is detectable or quantifiable at baseline (even if the value is negative).
 
Subjects will be (right-) censored at the last time observation of a detectable viral load. Subjects for which this last assessment is the baseline assessment will be censored at time 0.
 
(Date and time of event or censoring - date and time of first dose of study drug)/3600, rounded to one decimal.

Time to virus undetectable (hours) [interval censored]	
The time in hours from initiation of study treatment until the first post baseline time point at which the virus is undetectable, using interval censoring.
 
The boundaries of the censoring intervals are defined as the number of hours from the start of treatment.
 
The left boundary of the interval is the last positive assessment before the first confirmed negative sample which is not followed by a confirmed positive sample (at baseline every subject is considered positive). If no negative samples are observed, the left boundary will be the last sample obtained.
 
The right boundary of the interval is the first confirmed negative sample which is not followed by a confirmed positive sample. If this is not observed, the interval is right censored.
 
A confirmed positive sample is defined as two consecutive non-negative samples; a confirmed negative sample is defined as two consecutive negative samples.
 
Last obtained sample, whether positive or negative, is always

	considered confirmed.
--	-----------------------

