Proportion of subjects with undetectable RSV viral load

The proportion of subjects within the RSV RNA viral load categories (undetectable, detectable and quantifiable) will be shown in a frequency tabulation per analysis time point (with corresponding 95% CI), per treatment group and per phase (treatment, follow-up and combined treatment + follow-up).

Subjects with missing data on that analysis visit will not be counted in the denominator for the proportion.

In addition, a stratified logistic regression model will be used to analyze the outcome.

Time to peak viral load

This time-to event variable will be analyzed as indicated above using Kaplan-Meier analysis.

Time to virus undetectable [time-to event]

This time-to event variable will be analyzed as indicated above using Kaplan-Meier analysis.

Additionally, the time-to event data will be analyzed using the logrank test and Gehan-Wilcoxon method.

Time to virus undetectable [interval censored]

The differences in time to RSV RNA being undetectable of active dosing regimens versus placebo treatment will also be estimated using the accelerated failure time model based on interval censored data. Treatment and stratum will be added as fixed categorical effects, while log baseline viral load will be added as a continuous fixed covariate.

Treatment effect versus placebo will be reported as an acceleration factor including 95% confidence intervals for each active treatment group. Estimated survival curves will be created based on the mean baseline viral load value and weighted average for each stratum.

The baseline \log_{10} viral load will be included as the continuous covariate. Other covariates and or baseline indicators may be included in the model when of predictive value. The model building procedure will be used.

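### The fewer-than-10-events trigger for exact logistic regression checks one side only, so odds ratios for undetectable virus can be infinite when an arm is at 0% or 100%

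*SAP*

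**What the plan says.** Protocol section 2.1.2 lists among the secondary endpoints "Proportion of subjects with undetectable RSV viral load at each timepoint". SAP section 5.3.1.1 (Table 1) makes this binary: "Each RSV viral load measurement will be assigned to one of the 2 categories to identify if it is undetectable", with Yes coded 1 and No coded 0. The event is therefore clearance. After the per-visit frequency tables, SAP section 5.3.2.1 adds the model: "In addition, a stratified logistic regression model will be used to analyze the outcome".

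The model is defined in SAP section 5.3.2. It is logistic regression "with treatment group and stratification factors as fixed effect", and its output is set out as follows: "The odds ratios including 95% confidence interval of active groups versus placebo will be derived from the final model using appropriate contrasts". The only provision for sparse data is "Exact logistic regression models will be used in case the incidence of the events is low (< 10 events". The SAP does not say whether the 10 is pooled or per arm, or whether the confidence limits are Wald or profile-likelihood. It has no rule for few non-events, for an arm at 0% or 100%, or for a logistic model that fails to converge.

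**The concern.** Logistic regression treats events and non-events symmetrically: five children still detectable are as sparse as five children cleared. The rule counts only events. Because the event here is clearance, the count rises as the infection resolves, and the safeguard switches off as the other cell empties. A visit at which almost every child has cleared has far more than 10 events, so maximum likelihood is kept even when one arm has no detectable child. The same gap opens early if placebo has no cleared child but the active arms bring the total to 10 or more.

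At stake are the odds ratios with 95% confidence intervals promised for a listed secondary endpoint. An empty active arm spoils one comparison; an empty placebo arm spoils both. Without a stated rule, a rescue method would have to be chosen after the data are seen.

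**Working it through.** **Inputs.** The trigger and model terms come from SAP 5.3.2 and the coding from SAP 5.3.1.1. SAP 1.2.1 gives the planned maximum, "with 60 subjects planned per regimen". SAP 5.1.1 puts the expected final ITT-i set at 120, which is 120 / 3 = 40 per arm at 1:1:1. Losses reduce this further, since SAP 5.3.2.1 states: "Subjects with missing data on that analysis visit will not be counted in the denominator for the proportion". No document gives a clearance rate at any visit, so rates below are assumed over a range. The plan states no power or expected rate for this endpoint, so there is no figure of its own to reproduce.

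**1. Why the estimate diverges.** With n children per arm and a of them still detectable, the odds ratio of high dose versus placebo is [(n − a_H)/a_H] / [(n − a_P)/a_P]. If a_H = 0 and a_P > 0 it is infinite. The illustrations below omit the strata. Adding them does not rescue the estimate, because an arm with no detectable child has none in any stratum.

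Example: detectable 5/60 placebo, 2/60 low, 0/60 high. That is 55 + 58 + 60 = 173 events and 7 non-events, so the exact rule does not fire. High versus placebo:
- Maximum likelihood: log odds ratio 22.2, standard error 16,913, Wald p = 0.999.
- Fisher's exact test: p = 2 × C(60,5)/C(120,5) = 0.057.
- Penalised (0.5 added to each cell, which is Firth's result without covariates): (60.5/0.5) / (55.5/5.5) = 12.0.

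**2. The interval type matters.** With 56, 58 and 60 of 60 undetectable (174 events, 6 non-events), high versus placebo gives:
- Wald: 0 to infinity.
- Profile likelihood: 1.7 to infinity.
- Exact: 0.67 to infinity, with the odds ratio itself still infinite.
- Penalised odds ratio: (60.5/0.5) / (56.5/4.5) = 9.6.

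Low versus placebo in the same data is finite: (58/2)/(56/4) = 2.07, Wald interval 0.37 to 11.8. Few non-events alone do not cause the failure; an arm at exactly 0% or 100% does.

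**3. How often, late visits.** Let p be the undetectable rate, equal in all arms, and q = p^n the chance that one arm has no detectable child. At least one of three arms: 1 − (1 − q)³. A given active arm or placebo: 1 − (1 − q)². For p = 97% and n = 60, q = 0.161, giving 1 − 0.839³ = 41% and 1 − 0.839² = 30%.

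| Undetectable, all arms | q (40 / 60 per arm) | At least one arm | Given comparison |
|---|---|---|---|
| 90% | 0.015 / 0.002 | 4% / 0.5% | 3% / 0.4% |
| 95% | 0.129 / 0.046 | 34% / 13% | 24% / 9% |
| 97% | 0.296 / 0.161 | 65% / 41% | 50% / 30% |
| 98% | 0.446 / 0.298 | 83% / 65% | 69% / 51% |

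The column q is also the chance that placebo is the empty arm and both comparisons fail. With unequal rates of 90/95/97% (placebo/low/high), the at-least-one-arm figure is 40% / 20%. In none of these settings does the exact rule fire.

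**4. How often, early visits.** The chance of an infinite odds ratio with at least 10 events in total, by exact enumeration (40 / 60 per arm, placebo/low/high):
- 1% in all arms: about 0%, because the exact method is triggered.
- 5% in all arms: 0.3% / 1.1%.
- 2/5/8%: 1.6% / 7.9%.
- 5/15/20%: 12% / 4.6%.
- 2/12/15%: 29% / 29%.

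These use the pooled reading of the threshold. Read per arm, an arm with no events would trigger the exact method and the early gap would close; the late one would not. At middle visits (30% to 75% undetectable) the chance is about 0%.

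**The case against.** Four stronger readings are tempting, and the documents do not support them.

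- *Late-visit odds ratios will be infinite.* A reader might take near-complete clearance by Day 14 or 28 for granted, but neither document gives a rate. At 90% undetectable the failure is rare.
- *Few non-events are enough.* They are not, as the finite low-dose comparison above shows.
- *A real difference would be reported with p close to 1.* For the logistic model the SAP promises odds ratios with confidence intervals; it lists p-values only for the accelerated failure time model. Wald inference is an assumption, and profile limits keep a finite lower bound. In the first example Fisher's p is itself 0.057.
- *The endpoint is lost.* The model is an addition to per-arm frequency tables with 95% intervals, and time to undetectable virus is compared separately by log-rank, Gehan-Wilcoxon and interval-censored models.

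It is also fair to say that the rule suits most other outcomes that use this model (ICU need, ventilation, otitis media, death), where the event is normally the rarer category. And the at-least-one-arm figures overstate the loss for any single comparison; some of those trials also have both compared arms empty, with no observed difference to miss.

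All of this limits how often the problem arises and what depends on it. None of it supplies a rule for the case: nothing elsewhere in the SAP covers an arm at 0% or 100% once events reach 10.

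**Conclusion.** The point holds as a defect in a stated rule. The trigger measures sparsity on the event side only, and for an outcome coded so that success is the event it does not fire when non-events are few or an arm is full. The odds ratio versus placebo can then be infinite, and its interval uninformative if Wald limits are used.

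The size depends on clearance rates that the documents do not give. For a single comparison at 40 / 60 per arm, the risk runs from 3% / 0.4% at an assumed 90% undetectable to 69% / 51% at 98%. Early visits matter mainly if placebo clearance is near zero with about 12% or more on active; most sparse early visits already trigger the exact method. The effect is confined to a supplementary analysis of a secondary endpoint. The primary analysis is not touched.

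**What to change.** Replace the trigger sentence in SAP section 5.3.2 with:

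> Firth-penalised logistic regression, with profile-likelihood 95% confidence intervals, will be used when the smaller of the total number of events and non-events is below 10, or when any treatment arm has 0% or 100% events; exact logistic regression may be added as a sensitivity analysis.

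Naming one main method matters. Merely extending the exact method to few non-events would still leave the odds ratio and one limit infinite when an arm is empty, and the second example shows that the interval types can disagree about whether 1 is excluded. The wording also settles that the counts are pooled totals.

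The cost is one sentence and a standard method, with no new data; it should be settled before unblinding. The downside is that the penalised estimate is shrunk slightly toward no effect. Exact intervals, if added, are conservative and can have an infinite limit.
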